## **PASS/PAES** information

Title	C2C: COMBINE-2 for Cabotegravir+Rilpivirine LA Regimen - A Prospective Cohort Study to Monitor Effectiveness, Adherence and Resistance		
Protocol version identifier	v1.0		
Date of last version of protocol	[Date DD Month YYYY]		
EU PAS (ENCEPP) register number	Study not registered yet		
Active substance	Cabotegravir		
	Rilpivirine		
Medicinal product	VOCABRIA® 30 mg Film-coated tablets,  VOCABRIA® 400 mg prolonged release suspension for injection (2 mL)  VOCABRIA® 600 mg prolonged release suspension for injection.(3 mL)  Edurant® 25 mg film-coated tablets  Rekambys® 600 mg prolonged release suspension for injection. (2 mL)  Rekambys® 900 mg prolonged release suspension for injection. (3 mL)		
Product reference	Cabotegravir - EU/1/20/1481/001-003 Rilpivirine - EU/1/20/1482/001-002		
Procedure number	Cabotegravir - EMEA/H/4976 Rilpivirine - EMEA/H/5060		
Marketing	ViiV Healthcare B.V.		
authorisation Holder(s)	Janssen-Cilag International NV		
Joint PASS/PAES	Yes		

Research question and objectives	Following the initiation of CAB+RPV LA regimen among people living with HIV (PLWH), the study will aim to assess effectiveness, discontinuation, and resistance over a 24-month period of follow up in approximately 1000 PLWH.  Objectives:  1. Describe study population initiating CAB+RPV LA regimen, by baseline demographic and clinical characteristics  2. Assess adherence, durability and discontinuation for PLWH starting CAB+RPV LA regimen  3. Assess the clinical effectiveness (i.e. proportion of participants experiencing virologic failure) among PLWH who initiate CAB+RPV LA regimen and had suppressed viral load (VL <50 copies/mL) at regimen initiation  4. Monitor for resistance in case of VF while on CAB+RPV LA or after switching to a subsequent ARV regimen among individuals who switched off CAB+RPV LA regimen for any reason	
Country(-ies) of study	UK, Spain, Italy, France, Belgium, Germany, Sweden and additional countries to be determined after feasibility assessment	
Author	PPD , MBBS, MPH, PhD PPD , Epidemiology & Real World Evidence ViiV Healthcare [name] Email: PPD Phone: PPD	

## 1. LIST OF ABBREVIATIONS

ADE	AIDS-defining events
AE	adverse event
ART	antiretroviral treatment
ARV	antiretroviral
BCG	Bacille Calmette-Guérin
BMI	body mass index
CAB	Cabotegravir
CD4	cluster of differentiation four
CKD	chronic kidney disease
CVD	cardiovascular disease
DAA's	direct-acting antivirals
EC	ethics committee
EMA	European Medicines Agency
ESLD	end-stage liver disease
GI	gastrointestinal
HBV	hepatitis B virus
НСР	healthcare provider
HCV	hepatitis C virus
HIV	human immunodeficiency virus
INI	integrase inhibitor
INSTI	integrase strand transfer inhibitor
IQR	interquartile range
LA	long acting
LOD	limit of detection
MAH	marketing authorization holder
MTCT	mother-to-child transmission
NADM	non-AIDS-defining malignancy
NNRTI	non-nucleoside reverse transcriptase inhibitor
PI	principal investigator
PK	pharmacokinetics
PMTCT	prevention of mother-to-child transmission
RNA	ribonucleic acid
RPV	Rilpivirine
SmPC	summary of product characteristics
SoC	standard of care
STI	structured treatment interruption
ТВ	tuberculosis
UK	United Kingdom
VL	viral load

## **Trademark Information**

Trademarks of ViiV Healthcare and the GlaxoSmithKline group of companies
CABENUVATM
VOCABRIA TM

Trademarks not owned by ViiV Healthcare and the GlaxoSmithKline group of companies		
REKAMBYSTM		
EDURANT™		
SASTM		
SPSSTM		
STATATM		

#### 3. ABSTRACT

Cabotegravir (CAB), a human immunodeficiency virus type-1 (HIV-1) integrase strand transfer inhibitor (INSTI), in combination with Rilpivirine (RPV), an HIV-1 non-nucleoside reverse transcriptase inhibitor (NNRTI), is indicated as a complete regimen for the treatment of Human Immunodeficiency Virus type 1 (HIV-1) infection in adults who are virologically suppressed (HIV-1 RNA <50 copies/mL) on a stable antiretroviral (ARV) regimen without present or past evidence of viral resistance to, and no prior virological failure with agents of the NNRTI and INI class. Prior to the initiation of CAB long acting (LA) injection, CAB tablets together with RPV tablets should be taken for approximately one month (at least 28 days) to assess tolerability to CAB and RPV.

The gathering of real world evidence in routine clinical practice to evaluate effectiveness, discontinuation, and resistance would further demonstrate the value of this regimen.

The Marketing Authorization Holder (MAH) proposes a prospective cohort study to monitor for clinical effectiveness, discontinuation and resistance among PLWH receiving CAB+RPV LA in routine clinical practice. The proposed multi-site study "Real-world evidence for effectiveness of Two Drug Regimen, Antiretroviral therapy with integrase inhibitors plus a reverse transcriptase inhibitor Drug" (COMBINE-2) for the CAB+RPV LA regimen will be conducted through collaboration with NEAT ID Network, a well-established network of clinical sites across Europe.

Study Objectives: Following the initiation of CAB+RPV LA regimen among people living with HIV (PLWH), the study will aim to assess effectiveness, discontinuation, and resistance over 24-months of follow-up period in approximately 1000 PLWH.

The specific objectives are to:

- 1. Describe study population initiating CAB+RPV LA regimen, by baseline demographic and clinical characteristics
- 2. Assess adherence, durability and discontinuation for PLWH starting CAB+RPV LA regimen
- 3. Assess the clinical effectiveness (i.e. proportion individuals experiencing virologic failure) among study participants who initiate CAB+RPV LA regimen and had suppressed viral load (VL) at regimen initiation (<50 copies/mL)
- 4. Monitor for resistance in case of VF while on CAB+RPV LA or after switching to a subsequent ARV regimen among individuals who switched off CAB+RPV LA regimen for any reason over the 48 month follow up period.

## 4. AMENDMENTS AND UPDATES

Amendment or update no	Date	Section of study protocol	Amendment or update	Reason

## 5. MILESTONES

Milestone	Planned date
Draft Protocol Submission	Dec 31, 2020
Study Start (Protocol Approval)	Estimated - Jun 2021
1st Interim Report	Draft - Sep 2022
-	Final - Dec 2022
2 nd Interim Report	Draft - Sep 2023
-	Final - Dec 2023
3 rd Interim Report	Draft - Sep 2024
_	Final - Dec, 2024
4th Interim Report	Draft - Sep 2025
_	Final - Dec 2025
Data Collection Completion	Jun 2026 or 5 years following
	commercial availability of CAB
Final Report	Sep 2026
Supplemental Report	Depends on when the last individual
_	discontinuing the CAB+RPV LA
	regimen completes 4-years of follow up

#### 6. RATIONALE AND BACKGROUND

#### 6.1. Background

Cabotegravir (CAB), a human immunodeficiency virus type-1 (HIV-1) integrase strand transfer inhibitor (INSTI), in combination with Rilpivirine (RPV), an HIV-1 non-nucleoside reverse transcriptase inhibitor (NNRTI), is indicated as a complete regimen for the treatment of Human Immunodeficiency Virus type 1 (HIV-1) infection in adults who are virologically suppressed (HIV-1 RNA <50 copies/mL) on a stable antiretroviral (ARV) regimen without present or past evidence of viral resistance to, and no prior virological failure with agents of the NNRTI and INI class. Prior to the initiation of CAB long acting (LA) injection, CAB tablets together with RPV tablets should be taken for approximately one month (at least 28 days) to assess tolerability to CAB and RPV.

Treatment with CAB+RPV LA should be prescribed by a physician experienced in the management of HIV infection. Each injection should be administered by a healthcare provider (HCP). Prior to starting the regimen, the HCP should carefully select PLWH who agree to the required injection schedule and counsel individuals about the importance of adherence to scheduled dosing visits to help maintain viral suppression and reduce the risk of viral rebound and potential development of resistance associated with missed doses. Following discontinuation of CAB in combination with RPV injection, it is essential to adopt an alternative, fully suppressive ARV regimen per the summary of product characterization (SmPC).

The Marketing Authorization Holder (MAH) proposes a prospective cohort study to monitor for clinical effectiveness, discontinuation and resistance among PLWH receiving CAB+RPV LA in routine clinical practice. The proposed multi-site study "Real-world evidence for effectiveness of Two Drug Regimen, Antiretroviral therapy with integrase inhibitors plus a reverse transcriptase inhibitor Drug (COMBINE-2)" for the CAB+RPV LA regimen will be conducted through collaboration with NEAT ID Network, a well-established network of clinical sites across Europe.

The study will not require any changes to the standard of care that PLWH receive, and decisions on ARV treatment are made by the healthcare providers taking into account the treatment history, individual clinical characteristics and local guideline or recommendations. A detailed study protocol, once approved by EMA, will be implemented by the NEAT ID Network team.

#### 6.2. Rationale

Adherence to scheduled dosing visits to help maintain viral suppression and reduce the risk of viral rebound and potential development of resistance with missed doses is critical for long term maintenance of viral suppression with the regimen. Impact of non-adherence on virologic failure and emergence of resistance need to be assessed in real world clinical setting. Discontinuations for other reasons such as individual choice, drug interactions and pregnancy will also be captured. The gathering of this real world evidence would further demonstrate the value of this regimen.

### 7. RESEARCH QUESTION AND OBJECTIVE(S)

Following the initiation of CAB+RPV LA regimen among people living with HIV (PLWH), the study will aim to assess effectiveness, discontinuation, and resistance over 24-months of follow-up period in approximately 1000 participants.

The specific objectives are to:

- 1. Describe study population initiating CAB+RPV LA regimen, by baseline demographic and clinical characteristics
- 2. Assess adherence, durability and discontinuation for PLWH starting CAB+RPV LA regimen
  - Proportion of participants discontinuing the CAB+RPV LA regimen and lost to follow-up will be assessed.
    - Reasons for discontinuation will be assessed.
  - Non adherence to dosing schedule will be assessed by
    - a. Estimating the number of participants that missed one or more consecutive injections without taking daily oral bridging therapy or any other oral ARV regimen while not on CAB+RPV LA regimen and mean and median number of injections missed during a 12-month period
    - b. Estimating the number of participants who received the injections seven or more days later than their scheduled injection visit and median duration of delayed injections
- 3. Assess the clinical effectiveness (i.e. proportion of participants experiencing virologic failure) among PLWH who initiate CAB+RPV LA regimen and had suppressed viral load (VL <50 copies/mL) at regimen initiation
  - Estimate the proportion of participants with virologic failure, during the first 6 months after initiation of CAB+RPV LA regimen
  - Estimate the proportion of participants with virologic failure at 6, 12 and 24 months after initiation of CAB+RPV LA regimen
- 4. Monitor for resistance in case of VF while on CAB+RPV LA or after switching to a subsequent ARV regimen among individuals who switched off CAB+RPV LA regimen for any reason
  - Describe the ARV regimen participants are switched to after discontinuation of CAB+RPV LA regimen
  - Describe virologic outcomes at 12, 24, 36 and 48 months after discontinuation of CAB+RPV LA regimen
  - Monitor for virologic failure and resistance during the 48 months following the switch
    - Resistance test to be done for all participants with virologic failure during the follow-up period

 HIV subtype test to be done for participants with virologic failure during the follow-up period, if subtype data is not available

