### 8.4. Study size

The study will aim to enroll 1000 PLWH with VL <50 copies/mL, without present or past evidence of viral resistance to, and no prior virological failure with agents of the NNRTI and INI class initiating CAB+RPV LA regimen.

There is no formal statistical hypothesis to be tested in these analyses. The study will focus on absolute effectiveness estimation. Confidence intervals, constructed using the exact Clopper-Pearson method based on the cumulative probabilities of the binomial distribution, are presented in Table 2, 3, 4 and are designed to give estimates of precision.

It is anticipated that data from 1000 participants are thought adequate to meet the study objectives. In the ATLAS study in which participants switched from their PI, NNRTI, or INSTI based oral triple therapy regimen to CAB+RPV LA regimen, the percentage of participants with virologic failure (2 confirmed HIV RNA  $\geq$ 50 copies/mL) and treatment discontinuation were, respectively, 1.6% (95% CI 0.5 to 3.4) and 8.4% (95% CI 5.6 to 12.1) at week 48. Among the 3 individuals with confirmed virological failure, all selected drug resistance mutations. For resistance, we assume a 50% resistance rate at month-24 among those with virological failure.

With 1000 individuals, the precision for the estimation of virologic failure rate will range between 0.9 and 1.5% for a failure rate ranging from 2 to 6% as shown below in Table 2.

Confidence Level	Sample Size (N)	CI Width	Virologic Failure (P)	Lower Limit	Upper Limit
0.95	1000	0.019	0.02	0.012	0.031
0.95	1000	0.023	0.03	0.020	0.043
0.95	1000	0.025	0.04	0.029	0.054
0.95	1000	0.028	0.05	0.037	0.065
0.95	1000	0.031	0.06	0.046	0.077

The corresponding precision for the discontinuation rate will range between 1.7 to 2.3 for a rate ranging from 8 to 16% as shown below in Table 3.

Confidence Level	Sample Size (N)	CI Width	Discontinuation (P)	Lower Limit	Upper Limit
0.95	1000	0.035	0.08	0.064	0.099
0.95	1000	0.038	0.10	0.082	0.120
0.95	1000	0.041	0.12	0.101	0.142
0.95	1000	0.044	0.14	0.119	0.163
0.95	1000	0.046	0.16	0.138	0.184

If the virological failure rate is ranging from 2 to 6%, then the number of participants to be tested for genotypic resistance will range from 20 to 60 individuals. With these numbers of subjects, the precision for the estimation of resistance rate will range from 12.7% (with 60 individuals) to 21.9% (with 20 individuals) for resistance rate of 50%, as shown below in table 4.

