# AIM 3. Assess the clinical effectiveness among PLWH who initiate CAB+RPV LA regimen

Given that this study involves PLWH in routine clinical care, and who may not attend clinic appointments at 6, 12 or 24 months, a window of 12 weeks around the date in question will be used for virologic failure. Thus, the proportion with virologic failure during first six months, at 6, 12 or 24 months  $\pm$  6 weeks will be used; and if none is available, the first measurement during first six months, after 6, 12 or 24 months (and at most 6 weeks after the measurement).

Proportion of participants who continue to be suppressed (VL of <50 copies/mL) at each time point (after 6, 12 and 24 months of follow up) will be estimated, as well as proportion of individuals with VL of <200 copies/mL. CD4 counts will also be assessed. The proportion of participants with virologic failure (2 consecutive HIV RNA VL  $\geq$ 200 copies/mL or one HIV RNA VL level  $\geq$ 200 copies/mL followed by a discontinuation of CAB+RPV LA regimen) will be estimated and time to failure will be assessed by the Kaplan-Meier method. The two-sided 95% associated confidence interval will be calculated with Kalbfleisch and Prentice's formula. Time to event will be defined as the time between the date of the initiation of CAB+RPV LA regimen and the date of virologic failure. Follow-up will be censored at the analysis time point, or the date of last study contact, or date of discontinuation of CAB+RPV LA regimen, or the date of lost to follow-up, whichever will occur first.

Genotypic resistance testing will be performed in participants with confirmed HIV RNA VL  $\geq$ 200 copies/mL. Resistance interpretation will be given using the Stanford algorithm (https://hivdb.stanford.edu/hivdb/by-mutations). All drug resistance mutations identified will be described and number and percentage indicated. The proportion of participants with genotypic resistance viruses among those with virological failure will be estimated by the number of participants with genotypic resistance viruses divided by the total number of participants with virological failure. The associated two-sided 95% exact (Clopper–Pearson) confidence intervals will be calculated. The frequency of viral subtype among those with virologic failure will be reported.

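### Objective 3 asks what proportion of initiators fail, but Aim 3's only method with an interval is Kaplan-Meier censored at discontinuation, and the plan does not say which estimator answers the objective

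*Protocol*

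**What the plan says.** Section 7, objective 3, is to "Assess the clinical effectiveness (i.e. proportion of participants experiencing virologic failure) among PLWH who initiate CAB+RPV LA regimen", with the sub-objective "Estimate the proportion of participants with virologic failure at 6, 12 and 24 months after initiation of CAB+RPV LA regimen". Section 8.4 treats this as a simple proportion: exact binomial limits for 1000 participants, and a conversion of rates into counts that begins "If the virological failure rate is ranging from 2 to 6%, then the number of participants to be tested for genotypic resistance" and arrives at 20 to 60 people.

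Section 8.7, Aim 3, offers two routes to a failure figure. The first is a windowed quantity, "the proportion with virologic failure during first six months, at 6, 12 or 24 months", with a margin of 6 weeks; it has no stated denominator and no interval. The second is time to event: the proportion with failure "will be estimated and time to failure will be assessed by the Kaplan-Meier method". The next sentence reads "The two-sided 95% associated confidence interval will be calculated with Kalbfleisch and Prentice's formula", and it is the only interval given for failure. The censoring rule is "Follow-up will be censored at the analysis time point, or the date of last study contact, or date of discontinuation of CAB+RPV LA regimen", or loss to follow-up if that comes first.

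Aim 2 uses the same Kalbfleisch-Prentice interval for discontinuation proportions that it explicitly obtains by Kaplan-Meier.

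**The concern.** The objective and the study-size section describe a share of the people who start. One minus Kaplan-Meier with discontinuation censored is a different quantity. Someone who stops CAB+RPV LA without having failed cannot later fail on that regimen, but censoring treats that person as still exposed to the same future risk as those who stay. The same holds for someone who dies; Aim 3 does not name death, which would presumably be censored at last contact.

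The result is never below the proportion who fail on the regimen, and it is above it as soon as anyone stops before a later failure. A larger sample does not remove the gap. Since the study aims at absolute estimation, this affects its main effectiveness figure, and a reported rate times 1000 would no longer give the number of failures, which Aim 3 uses as the denominator for resistance.

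**Working it through.** **1. The plan's own figures.** Exact Clopper-Pearson limits for N = 1000 reproduce Tables 2 and 3 of section 8.4. Failure at 2% gives 0.012 to 0.031 (half-width 0.92 points). At 4% the half-width is 1.27 points. At 6% the limits are 0.046 to 0.077 (half-width 1.52 points). Discontinuation at 8% and 16% gives half-widths of 1.73 and 2.32 points. These are intervals for x/1000, not for a Kaplan-Meier estimate.

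**2. Inputs.** Let v be the proportion who fail on the regimen by the time point (2% to 6%, section 8.4). Let d be the proportion who stop without prior failure by the same time point (8% to 16%, section 8.4). Two assumptions are mine. The protocol ties neither range to a time point. Its 8-16% is also total discontinuation, and because stopping after one viral load of 200 copies/mL or more is itself a failure event, 8-16% is an upper reading of d.

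**3. Formula, constant hazards.** The total cumulative hazard is L = -ln(1 - v - d). The failure share is h = L × v/(v + d). Then 1-KM = 1 - exp(-h), to be compared with v.

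For v = 6%, d = 16%: L = -ln(0.78) = 0.2485; h = 0.2485 × 6/22 = 0.0678; 1-KM = 6.55%. For v = 2%, d = 8%: L = -ln(0.90) = 0.1054; h = 0.1054 × 2/10 = 0.0211; 1-KM = 2.09% (2.085% before rounding).

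| v | d | 1-KM | Excess (points) | Relative | Share of half-width |
|---|---|---|---|---|---|
| 2% | 8% | 2.09% | 0.09 | 4% | 9% |
| 2% | 16% | 2.18% | 0.18 | 9% | 20% |
| 4% | 12% | 4.27% | 0.27 | 7% | 21% |
| 6% | 8% | 6.26% | 0.26 | 4% | 17% |
| 6% | 16% | 6.55% | 0.55 | 9% | 36% |

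In counts, the last row reports 0.0655 × 1000, about 66 failures, when 60 participants fail.

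**4. Timing.** If all stopping came before any failure, 1-KM would reach v/(1 - d): 0.02/0.92 = 2.17% at the low end (excess 0.17) and 0.06/0.84 = 7.14% at the high end (excess 1.14). If all stopping came after the last failure, the excess would be zero. The constant-hazard figures lie between these limits.

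**5. Simulation.** With v = 6%, d = 16%, N = 1000 and 2000 runs, the mean 1-KM was 6.57% against a mean observed proportion of 6.01%. 1-KM was the larger in every run.

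**6. Strata.** Section 8.7 stratifies results by dosing interval and presents hepatitis co-infection separately. With 4% failing in both strata, 8% stopping gives 1-KM of 4.17% (L = -ln(0.88) = 0.1278, h = 0.0426). With 16% stopping it gives 4.36% (L = -ln(0.80) = 0.2231, h = 0.0446).

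**The case against.** The strongest reply is that Kaplan-Meier is grammatically attached to time to failure, that Aim 3 also defines a windowed proportion at the objective's own time points, and that binomial planning in section 8.4 fits a crude proportion. On that view the objective is answered elsewhere, and an on-regimen curve censored at discontinuation is a sound measure of a regimen's durability. Part of this stands: the text does not plainly say that the reported proportion is 1-KM. But the windowed figure has no denominator or interval, whereas the resistance proportion in Aim 3 and the suppression proportion in Aim 4 have both. Aim 2's parallel wording also points towards 1-KM. A coherent curve does not make it the proportion the objective asks for.

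A reader might infer four stronger points that the documents do not support:

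- **That the plan estimates the risk if nobody stopped.** This requires stopping to be unrelated to failure risk. The stopping reasons in section 8.3.2 include partial virological failure (1.2), non-adherence (22) and confirmed low-level viraemia (28), so 1-KM may estimate neither quantity.
- **That strata with more stopping look worse even at the same on-regimen failure hazard.** They do not, since 1 - exp(-h) depends on the failure hazard alone. The cumulative incidence is what differs there: with 1-KM at 6.0% in both strata and stopping hazards equivalent to 8% and 24% discontinuation, it is 5.76% and 5.25%.
- **That 1-KM exceeds all failures among initiators.** The direction is settled only for failure on the regimen. If failures after the switch were counted, it would be undetermined.
- **That the excess approaches 0.9 points.** This comes from extrapolating the cited 8.4% at week 48 at a constant hazard (1 - 0.916^(104/48) = 17.3%, or 24.4% from its upper limit) and then placing half the stopping hazard in the first 6 months. The two assumptions conflict. With that front-loading, week 48 already carries 0.5 + 0.5 × 22/78 = 64% of the 24-month hazard, so 8.4% implies about 12.8%, inside the protocol's own range.

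**Conclusion.** The point holds as a mismatch between objective and estimator that the protocol itself creates, since it fixes both the method and the censoring rule. Two non-equivalent failure figures stand side by side, and the one with an interval does not estimate the share of initiators who fail on the regimen.

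If 1-KM is the reported figure, it is too high for that purpose by about 0.09 to 0.55 points (4% to 9% relative). This rests on constant hazards and on taking 8-16% as discontinuation without prior failure at the same time point as the failure rate. Fewer such stops would shrink it, and earlier stopping would enlarge it. The study tests no hypothesis and the gap is well inside the interval, so no conclusion is overturned. It should still be corrected, because the gap runs in one direction and the correction is cheap.

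**What to change.** In section 8.7, Aim 3, name one estimator for objective 3: the Aalen-Johansen cumulative incidence of on-regimen virologic failure by 6, 12 and 24 months, with its 95% confidence interval, taking discontinuation without failure and death as competing events. Loss to follow-up stays censored. Failure after the switch stays under objective 4. Keep the Kaplan-Meier curve with its Kalbfleisch-Prentice interval as a supplement labelled as on-regimen and censored at discontinuation; it also serves comparisons of the on-regimen failure hazard between strata. State the role of the windowed proportion.

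The cost is a change of wording and one additional procedure. The case report form in Annex 1 already collects the date and reason of discontinuation, the date and reason of withdrawal including death, and dated viral loads. The downside is that two curves must be explained to readers.
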